14.1 Description of Study Subjects

14.1.1 Disposition of Subjects

Table 8: Subject Disposition by Treatment Group

[Implementation Note: Percentages are calculated using the denominators displayed in the header. Listings should be referenced by title for clarity.]

Subject Disposition	Group A: 100 µg Sm-p80 (unadjuvanted) (N=X)		Group B: 10 µg Sm-p80 + 5 µg GLA-SE (N=X)		Group C: 30 µg Sm-p80 + 5 µg GLA-SE (delayed booster) (N=X)		Group D: 30 µg Sm-p80 + 5 µg GLA-SE (N=X)		Group E: 10 µg Sm-p80 + 5 µg GLA-SE (N=X)		All Subjects (N=X)	
	n	%	n	%	n	%	n	%	n	%	n	%
Screened	--	--	--	--	--	--	--	--	--	--	x	--
Enrolled/Randomized	x	100	x	100	x	100	x	100	x	100	x	100
Received One Scheduled Treatment	x	xx	x	xx	x	xx	x	xx	x	xx	x	xx
Received Two Scheduled Treatments	x	xx	x	xx	x	xx	x	xx	x	xx	x	xx
Received All Scheduled Treatments ^a	x	xx	x	xx	x	xx	x	xx	x	xx	x	xx
Completed All Safety Blood Draws Groups A, B, D, E [Days 1, 8, 29, 36, 57, 64, 85] Group C [Days 1, 8, 29, 36, 57, 180, 187, 208]												
Completed All Immunogenicity Blood Draws for Antibody Assays Groups A, B, D, E [Days 1, 8, 29, 36, 57, 64, 85, 181] Group C [Days 1, 8, 29, 36, 57, 180, 187, 208, 304]												
Completed Follow-up ^a Groups A, B, D, E (Study Day 422) Group C (Study Day 545)												
Completed Per Protocol ^b												

Note: N = Number of subjects enrolled to the specified treatment group.

^a Refer to Listing 16.2.1 for reasons subjects discontinued or terminated early.

^b Refer to Listing 16.2.3 for reasons subjects are excluded from the Analysis populations .

Table 9: Analysis Populations by Treatment Group

Analysis Populations	Reason Subjects Excluded	Group A: 100 µg Sm-p80 (unadjuvanted) (N=X)		Group B: 10 µg Sm-p80 + 5 µg GLA-SE (N=X)		Group C: 30 µg Sm-p80 + 5 µg GLA-SE (delayed booster) (N=X)		Group D: 30 µg Sm-p80 + 5 µg GLA-SE (N=X)		Group E: 100 µg Sm-p80 + 5 µg GLA-SE (N=X)		All Subjects (N=X)	
		n	%	n	%	n	%	n	%	n	%	%	n
Safety Population	Any Reason	x	xx	x	xx	x	xx	x	xx	x	xx	x	xx
	Did not receive study product												
	[Reason 2]												
mITT Immunogenicity Population	Any Reason												
	Did not have post-baseline immunogenicity assay												
	[Reason 2]												
Per Protocol Population	Any Reason												
	Did not have post-baseline immunogenicity assay												
	Found to be ineligible at baseline after the enrollment												
	[Reason 3]												

Note: N = Number of subjects enrolled to the specified treatment group. Subjects may be counted for more than one reason but will only be counted up to one time for "Any Reason" per population.

Table 10: Dates of First Treatment by Treatment Group

Dates of Dosing	Group A: 100 µg Sm-p80 (unadjuvanted) (N=X)	Group B: 10 µg Sm-p80 + 5 µg GLA-SE (N=X)	Group C: 30 µg Sm-p80 + 5 µg GLA-SE (delayed booster) (N=X)	Group D: 30 µg Sm-p80 + 5 µg GLA-SE (N=X)	Group E: 10 µg Sm-p80 + 5 µg GLA-SE (N=X)	All Subjects (N=X)
Total (Entire period of enrollment)						
DDMMYYYY-DDMMYYYY [categorize based on length of enrollment period]	x	x	x	x	x	x

Note: N = Number of subjects enrolled to the specified treatment group.

Table 11: Ineligibility Summary of Screen Failures[Implementation Note: Inclusion and exclusion criteria are listed in **Section 4.3.**]

Inclusion/Exclusion Category	Inclusion/Exclusion Criterion	n ^a	% ^b
Inclusion and Exclusion	Number of subjects failing any eligibility criterion	x	100
Inclusion	Any inclusion criterion	x	xx
	[inclusion criterion 1]	x	xx
	[inclusion criterion 2]	x	xx
	[inclusion criterion 3]	x	xx
Exclusion	Any exclusion criterion	x	xx
	[exclusion criterion 1]	x	xx
	[exclusion criterion 2]	x	xx
	[exclusion criterion 3]	x	xx
Eligible but not enrolled	[Reason 1]	x	xx
	[Reason 2]	x	xx

^a More than one criterion may be marked per subject.^b Denominator for percentages is the total number of screen failures.

14.1.2 Demographic Data by Study Group

Table 12: Summary of Categorical Demographic and Baseline Characteristics by Treatment Group, All Enrolled Subjects

Variable	Characteristic	Group A: 100 µg Sm-p80 (unadjuvanted) (N=X)		Group B: 10 µg Sm-p80 + 5 µg GLA-SE (N=X)		Group C: 30 µg Sm-p80 + 5 µg GLA-SE (delayed booster) (N=X)		Group D: 30 µg Sm-p80 + 5 µg GLA-SE (N=X)		Group E: 100 µg Sm-p80 + 5 µg GLA-SE (N=X)		All Subjects (N=X)	
		n	%	n	%	n	%	n	%	n	%	n	%
Sex	Male	x	xx	x	xx	x	xx	x	xx	x	xx	x	xx
	Female												
Ethnicity	Not Hispanic or Latino	x	xx	x	xx	x	xx	x	xx	x	xx	x	xx
	Hispanic or Latino												
	Not Reported												
	Unknown												
Race	American Indian or Alaska Native	x	xx	x	xx	x	xx	x	xx	x	xx	x	xx
	Asian												
	Native Hawaiian or Other Pacific Islander												
	Black or African American												
	White												
	Multi-Racial												
	Unknown												

Note: N = Number of subjects in the Safety Population.

Table 13: Summary of Continuous Demographic and Baseline Characteristics by Treatment Group

Variable	Statistic	Group A: 100 µg Sm-p80 (unadjuvanted) (N=X)	Group B: 10 µg Sm-p80 + 5 µg GLA-SE (N=X)	Group C: 30 µg Sm-p80 + 5 µg GLA-SE (delayed booster) (N=X)	Group D: 30 µg Sm-p80 + 5 µg GLA-SE (N=X)	Group E: 100 µg Sm-p80 + 5 µg GLA-SE (N=X)	All Subjects (N=X)
Age (years)	Mean	xx	xx	xx	xx	xx	xx
	Standard Deviation	xx	xx	xx	xx	xx	xx
	Median	x	x	x	x	x	x
	Minimum	x	x	x	x	x	x
	Maximum	x	x	x	x	x	x
Height (cm)	Mean						
	Standard Deviation						
	Median						
	Minimum						
	Maximum						
Weight (kg)	Mean						
	Standard Deviation						
	Median						
	Minimum						
	Maximum						
BMI (kg/m ²)	Mean						
	Standard Deviation						
	Median						
	Minimum						
	Maximum						

Note: N = Number of subjects in the Safety Population.

14.1.3 Prior and Concurrent Medical Conditions

Table 14: Summary of Subjects with Pre-Existing Medical Conditions by MedDRA System Organ Class and Treatment Group

MedDRA System Organ Class	Group A: 100 µg Sm-p80 (unadjuvanted) (N=X)		Group B: 10 µg Sm-p80 + 5 µg GLA-SE (N=X)		Group C: 30 µg Sm-p80 + 5 µg GLA-SE (delayed booster) (N=X)		Group D: 30 µg Sm-p80 + 5 µg GLA-SE (N=X)		Group E: 100 µg Sm-p80 + 5 µg GLA-SE (N=X)		All Subjects (N=X)	
	n	%	n	%	n	%	n	%	n	%	n	%
Any SOC	x	xx	x	xx	x	xx	x	xx	x	xx	x	xx
[SOC 1]												
[SOC 2]												
[SOC 3]												

Note: N = Number of subjects in the Safety Population; n = Number of subjects reporting medical history within the specified SOC. A subject is only counted once per SOC.

14.2 Immunogenicity Data

Table 15: Anti-Sm-p80 ELISA Total IgG Geometric Mean Titers (GMT) Results with 95% Confidence Intervals by Time Point and Treatment Group, mITT Immunogenicity Population

Time Point	Statistic	Group A: 100 µg Sm-p80 (unadjuvanted) (N=X)	Group B: 10 µg Sm-p80 + 5 µg GLA-SE (N=X)	Group C: 30 µg Sm-p80 + 5 µg GLA-SE (delayed booster) (N=X)	Group D: 30 µg Sm-p80 + 5 µg GLA-SE (N=X)	Group E: 100 µg Sm-p80 + 5 µg GLA-SE (N=X)
Study Day 1 (Pre-Dose 1) (Baseline)	n	x	x	x	x	x
	GMT (95% CI)	x.x (x.x, x.x)	x.x (x.x, x.x)	x.x (x.x, x.x)	x.x (x.x, x.x)	x.x (x.x, x.x)
	Mean	x.x	x.x	x.x	x.x	x.x
	Std. Dev.	x.x	x.x	x.x	x.x	x.x
	Median	x.x	x.x	x.x	x.x	x.x
	(Minimum, Maximum)	(x.x, x.x)	(x.x, x.x)	(x.x, x.x)	(x.x, x.x)	(x.x, x.x)
Study Day 8 (7 Days Post Dose 1)	n					
	GMT (95% CI)					
	Mean					
	Std. Dev.					
	Median					
	(Minimum, Maximum)					
Study Day 29 (28 Days Post Dose 1; Pre-Dose 2)	n					
	GMT (95% CI)					
	Mean					

Table 15: Anti-Sm-p80 ELISA Total IgG Geometric Mean Titers (GMT) Results with 95% Confidence Intervals by Time Point and Treatment Group, mITT Immunogenicity Population (Continued)

Time Point	Statistic	Group A: 100 µg Sm-p80 (unadjuvanted) (N=X)	Group B: 10 µg Sm-p80 + 5 µg GLA-SE (N=X)	Group C: 30 µg Sm-p80 + 5 µg GLA-SE (delayed booster) (N=X)	Group D: 30 µg Sm-p80 + 5 µg GLA- SE (N=X)	Group E: 100 µg Sm-p80 + 5 µg GLA-SE (N=X)
	Std. Dev.					
	Median					
	(Minimum, Maximum)					
Study Day 36 (7 Days Post Dose 2)	n					
	GMT (95% CI)					
	Mean					
	Std. Dev.					
	Median					
	(Minimum, Maximum)					
Study Day 57 (Groups A, B, D, E: 28 Days Post Dose 2; Pre-Dose 3) (Group C: 28 Days Post Dose 2)	n					
	GMT (95% CI)					
	Mean					
	Std. Dev.					
	Median					
	(Minimum, Maximum)					
Study Day 64 (Groups A, B, D, E: 7 Days Post Dose 3)	n				N/A	

Table 15: Anti-Sm-p80 ELISA Total IgG Geometric Mean Titers (GMT) Results with 95% Confidence Intervals by Time Point and Treatment Group, mITT Immunogenicity Population (Continued)

Time Point	Statistic	Group A: 100 µg Sm-p80 (unadjuvanted) (N=X)	Group B: 10 µg Sm-p80 + 5 µg GLA-SE (N=X)	Group C: 30 µg Sm-p80 + 5 µg GLA-SE (delayed booster) (N=X)	Group D: 30 µg Sm-p80 + 5 µg GLA- SE (N=X)	Group E: 100 µg Sm-p80 + 5 µg GLA-SE (N=X)
	GMT (95% CI)			N/A		
	Mean			N/A		
	Std. Dev.			N/A		
	Median			N/A		
	(Minimum, Maximum)			N/A		
Study Day 85 (Groups A, B, D, E: 28 Days Post Dose 3)	n			N/A		
	GMT (95% CI)			N/A		
	Mean			N/A		
	Std. Dev.			N/A		
	Median			N/A		
	(Minimum, Maximum)			N/A		
Study Day 180 (Group C: Pre-Dose 3)	n	N/A	N/A		N/A	N/A
	GMT (95% CI)	N/A	N/A		N/A	N/A
	Mean	N/A	N/A		N/A	N/A
	Std. Dev.	N/A	N/A		N/A	N/A
	Median	N/A	N/A		N/A	N/A
	(Minimum, Maximum)	N/A	N/A		N/A	N/A

Table 15: Anti-Sm-p80 ELISA Total IgG Geometric Mean Titers (GMT) Results with 95% Confidence Intervals by Time Point and Treatment Group, mITT Immunogenicity Population (Continued)

Time Point	Statistic	Group A: 100 µg Sm-p80 (unadjuvanted) (N=X)	Group B: 10 µg Sm-p80 + 5 µg GLA-SE (N=X)	Group C: 30 µg Sm-p80 + 5 µg GLA-SE (delayed booster) (N=X)	Group D: 30 µg Sm-p80 + 5 µg GLA- SE (N=X)	Group E: 100 µg Sm-p80 + 5 µg GLA-SE (N=X)
Study Day 187 (Group C: 7 Days Post Dose 3)	n	N/A	N/A		N/A	N/A
	GMT (95% CI)	N/A	N/A		N/A	N/A
	Mean	N/A	N/A		N/A	N/A
	Std. Dev.	N/A	N/A		N/A	N/A
	Median	N/A	N/A		N/A	N/A
	(Minimum, Maximum)	N/A	N/A		N/A	N/A
Study Day 181 (Groups A, B, D, E: 124 Days Post Dose 3)	n			N/A		
	GMT (95% CI)			N/A		
	Mean			N/A		
	Std. Dev.			N/A		
	Median			N/A		
	(Minimum, Maximum)			N/A		
Study Day 208 (Group C: 28 Days Post Dose 3)	n	N/A	N/A		N/A	N/A
	GMT (95% CI)	N/A	N/A		N/A	N/A
	Mean	N/A	N/A		N/A	N/A

Table 15: Anti-Sm-p80 ELISA Total IgG Geometric Mean Titers (GMT) Results with 95% Confidence Intervals by Time Point and Treatment Group, mITT Immunogenicity Population (Continued)

Time Point	Statistic	Group A: 100 µg Sm-p80 (unadjuvanted) (N=X)	Group B: 10 µg Sm-p80 + 5 µg GLA-SE (N=X)	Group C: 30 µg Sm-p80 + 5 µg GLA-SE (delayed booster) (N=X)	Group D: 30 µg Sm-p80 + 5 µg GLA- SE (N=X)	Group E: 100 µg Sm-p80 + 5 µg GLA-SE (N=X)
	Std. Dev.	N/A	N/A		N/A	N/A
	Median	N/A	N/A		N/A	N/A
	(Minimum, Maximum)	N/A	N/A		N/A	N/A
Study Day 304 (Group C: 124 Days Post Dose 3)	n	N/A	N/A		N/A	N/A
	GMT (95% CI)	N/A	N/A		N/A	N/A
	Mean	N/A	N/A		N/A	N/A
	Std. Dev.	N/A	N/A		N/A	N/A
	Median	N/A	N/A		N/A	N/A
	(Minimum, Maximum)	N/A	N/A		N/A	N/A

Note: N = Number of subjects in the mITT Immunogenicity Population; n = Number of subjects with results at the given time point. GMT = Geometric mean titer.

Pseudo Code:

```
/*Geometric Mean Titers*/
data dsn2;
  set dsn1;
  log_aval = log(aval);
proc means data=dsn2 n mean clm noint;
  by stdy trta;
  var log_aval;
  output out= gmt0(drop=_type_ _freq_)
    n= n
    mean= mean
    std= sd
    median= med
    max= max
    min= min
    lclm=lclm
    uclm=uclm;
data gmt;
  set gmt0;
  gmt = put(exp(mean),8.1); /*geometric mean titer*/
  gmt_l = put(exp(lclm), 8.1); /*lower bound*/
  gmt_u = put(exp(uclm), 8.1); /*upper bound*/
  gmt_ci = strip(gmt)||' ('||strip(gmt_l)||', '||strip(gmt_u)||')'; /*GMT(95% CI)*/
  gmt_mm = ' ('||strip(min)||', '||strip(max)||')'; /*(Min, Max)*/
run;
```

Table 16: Anti-Sm-p80 ELISA Total IgG Geometric Mean Fold Rise (GMFR) and Seroconversion Results by Time Point and Treatment Group, mITT Immunogenicity Population

Time Point	Statistic	Group A: 100 µg Sm-p80 (unadjuvanted) (N=X)	Group B: 10 µg Sm-p80 + 5 µg GLA-SE (N=X)	Group C: 30 µg Sm-p80 + 5 µg GLA-SE (delayed booster) (N=X)	Group D: 30 µg Sm-p80 + 5 µg GLA-SE (N=X)	Group E: 100 µg Sm-p80 + 5 µg GLA-SE (N=X)
Study Day 8 (7 Days Post Dose 1)	n	x	x	x	x	x
	GMFR ^a (95% CI)	x.x (x.x, x.x)	x.x (x.x, x.x)	x.x (x.x, x.x)	x.x (x.x, x.x)	x.x (x.x, x.x)
	Number (%) of Responders ^b	x (xx)	x (xx)	x (xx)	x (xx)	x (xx)
	95% CI	x.x, x.x	x.x, x.x	x.x, x.x	x.x, x.x	x.x, x.x
Study Day 29 (28 Days Post Dose 1; Pre-Dose 2)	n	x	x	x	x	x
	GMFR ^a (95% CI)	x.x (x.x, x.x)	x.x (x.x, x.x)	x.x (x.x, x.x)	x.x (x.x, x.x)	x.x (x.x, x.x)
	Number (%) of Responders ^b	x (xx)	x (xx)	x (xx)	x (xx)	x (xx)
	95% CI	x.x, x.x	x.x, x.x	x.x, x.x	x.x, x.x	x.x, x.x
Study Day 36 (7 Days Post Dose 2)	n	x	x	x	x	x
	GMFR ^a (95% CI)	x.x (x.x, x.x)	x.x (x.x, x.x)	x.x (x.x, x.x)	x.x (x.x, x.x)	x.x (x.x, x.x)
	Number (%) of Responders ^b	x (xx)	x (xx)	x (xx)	x (xx)	x (xx)
	95% CI	x.x, x.x	x.x, x.x	x.x, x.x	x.x, x.x	x.x, x.x
Study Day 57 (Groups A, B, D, E: 28 Days Post Dose 2; Pre-Dose 3) (Group C: 28 Days Post Dose 2)	n	x	x	x	x	x
	GMFR ^a (95% CI)	x.x (x.x, x.x)	x.x (x.x, x.x)	x.x (x.x, x.x)	x.x (x.x, x.x)	x.x (x.x, x.x)
	Number (%) of Responders ^b	x (xx)	x (xx)	x (xx)	x (xx)	x (xx)
	95% CI	x.x, x.x	x.x, x.x	x.x, x.x	x.x, x.x	x.x, x.x

Table 16: Anti-Sm-p80 ELISA Total IgG Geometric Mean Fold Rise (GMFR) and Seroconversion Results by Time Point and Treatment Group, mITT Immunogenicity Population (Continued)

Time Point	Statistic	Group A: 100 µg Sm-p80 (unadjuvanted) (N=X)	Group B: 10 µg Sm-p80 + 5 µg GLA-SE (N=X)	Group C: 30 µg Sm-p80 + 5 µg GLA-SE (delayed booster) (N=X)	Group D: 30 µg Sm-p80 + 5 µg GLA-SE (N=X)	Group E: 100 µg Sm-p80 + 5 µg GLA-SE (N=X)
Study Day 64 (Groups A, B, D, E: 7 Days Post Dose 3)	n	x	x	N/A	x	x
	GMFR ^a (95% CI)	x.x (x.x, x.x)	x.x (x.x, x.x)	N/A	x.x (x.x, x.x)	x.x (x.x, x.x)
	Number (%) of Responders ^b	x (xx)	x (xx)	N/A	x (xx)	x (xx)
	95% CI	x.x, x.x	x.x, x.x	N/A	x.x, x.x	x.x, x.x
Study Day 85 (Groups A, B, D, E: 28 Days Post Dose 3)	n	x	x	N/A	x	x
	GMFR ^a (95% CI)	x.x (x.x, x.x)	x.x (x.x, x.x)	N/A	x.x (x.x, x.x)	x.x (x.x, x.x)
	Number (%) of Responders ^b	x (xx)	x (xx)	N/A	x (xx)	x (xx)
	95% CI	x.x, x.x	x.x, x.x	N/A	x.x, x.x	x.x, x.x
Study Day 180 (Group C: Pre-Dose 3)	n	N/A	N/A	x	N/A	N/A
	GMFR ^a (95% CI)	N/A	N/A	x.x (x.x, x.x)	N/A	N/A
	Number (%) of Responders ^b	N/A	N/A	x (xx)	N/A	N/A
	95% CI	N/A	N/A	x.x, x.x	N/A	N/A
Study Day 187 (Group C: 7 Days Post Dose 3)	n	N/A	N/A	x	N/A	N/A
	GMFR ^a (95% CI)	N/A	N/A	x.x (x.x, x.x)	N/A	N/A
	Number (%) of Responders ^b	N/A	N/A	x (xx)	N/A	N/A
	95% CI	N/A	N/A	x.x, x.x	N/A	N/A
Study Day 181 (Groups A, B, D, E: 124 Days Post Dose 3)	n	x	x	N/A	x	x

Table 16: Anti-Sm-p80 ELISA Total IgG Geometric Mean Fold Rise (GMFR) and Seroconversion Results by Time Point and Treatment Group, mITT Immunogenicity Population (Continued)

Time Point	Statistic	Group A: 100 µg Sm-p80 (unadjuvanted) (N=X)	Group B: 10 µg Sm-p80 + 5 µg GLA-SE (N=X)	Group C: 30 µg Sm-p80 + 5 µg GLA-SE (delayed booster) (N=X)	Group D: 30 µg Sm-p80 + 5 µg GLA-SE (N=X)	Group E: 100 µg Sm-p80 + 5 µg GLA-SE (N=X)
	GMFR ^a (95% CI)	x.x (x.x, x.x)	x.x (x.x, x.x)	N/A	x.x (x.x, x.x)	x.x (x.x, x.x)
	Number (%) of Responders ^b	x (xx)	x (xx)	N/A	x (xx)	x (xx)
	95% CI	x.x, x.x	x.x, x.x	N/A	x.x, x.x	x.x, x.x
Study Day 208 (Group C: 28 Days Post Dose 3)	n	N/A	N/A	x	N/A	N/A
	GMFR ^a (95% CI)	N/A	N/A	x.x (x.x, x.x)	N/A	N/A
	Number (%) of Responders ^b	N/A	N/A	x (xx)	N/A	N/A
	95% CI	N/A	N/A	x.x, x.x	N/A	N/A
Study Day 304 (Group C: 124 Days Post Dose 3)	n	N/A	N/A	x	N/A	N/A
	GMFR ^a (95% CI)	N/A	N/A	x.x (x.x, x.x)	N/A	N/A
	Number (%) of Responders ^b	N/A	N/A	x (xx)	N/A	N/A
	95% CI	N/A	N/A	x.x, x.x	N/A	N/A

Note: N = Number of subjects in the mITT Immunogenicity Population; n = Number of subjects with results at the given timepoint.

^a GMFR represents the geometric mean fold rise in antibody compared to pre-dose 1.^b Number of responders represents the percentage of subjects with at least a 4-Fold Rise in antibody compared to Day 1, pre-dose 1.

Pseudo Code:

```
/*Geometric Mean Fold Rise*/
data dsn2;
  set dsn1;
  log_fold = log(mchg);
proc means data= dsn2 n mean clm noint;
  by stdy trta;
  var log_fold;
  output out= gmfr0(drop= _type_ _freq_)
    n= n2
    mean= mean
    lclm= lclm
    uclm= uclm;
data gmfr;
  set gmfr0;
  gmfr = put(exp(mean),8.1);                                     /*geometric mean fold rise*/
  gmfr_l = put(exp(lclm), 8.1);                                  /*lower bound*/
  gmfr_u = put(exp(uclm), 8.1);                                  /*upper bound*/
  gmfr_ci = strip(gmfr)||' ('||strip(gmfr_l)||', '||strip(gmfr_u)||')'; /*GMFR(95%CI)*/
run;

/*Seroresponders*/
proc freq data= dsn1 noint;
  table stdy*trta / out= totcnt(keep= stdy trta count rename= count=totcnt);

proc freq data= dsn1 noint;
  where crit1fl ^= ''; /*seroconversion flag = Y*/
  table stdy*trta / out= cnt(keep= stdy trta count);
```

Pseudo Code (*continued*):

```
data cntp;
merge cnt totcnt;
by stdy trta;
  if count=. then count=0;
  scn = put(count/totcnt*100, 5.1);
data cntci;
set cntp;
  sym = 1;           /*seroconversion*/
output;
  sym = 0;           /*no seroconversion*/
  count = totcnt - count;
output;
proc freq data= cntci;
by stdy trta;
tables sym / nocum norow binomial(cl= wilson);
weight count;           /*zeros: for CI of zero*/
  *exact binomial;
ods output binomial= binany (keep=stdy trta name1 nvalue1 where=(name1 in ('XL_BIN','XU_BIN')));
run;
```

Table 17: Comparison of Anti-Sm-p80 ELISA Total IgG Seroresponse Rates between Group A and Each Treatment Group 28-Days Post Dose – mITT Immunogenicity Population

Analysis Population	Dose	Statistic	Group A: 100 µg Sm-p80 (unadjuvanted) (N=X)	Group B: 10 µg Sm-p80 + 5 µg GLA-SE (N=X)	Group C: 30 µg Sm-p80 + 5 µg GLA-SE (delayed booster) (N=X)	Group D: 30 µg Sm-p80 + 5 µg GLA-SE (N=X)	Group E: 100 µg Sm-p80 + 5 µg GLA-SE (N=X)
mITT Immunogenicity Population	1	Fraction Responders, n ^a	x	x	x	x	x
		Responders, Rate	xx%	xx%	xx%	xx%	xx%
		95% CI ^b	x.XXX, x.XXX	x.XXX, x.XXX	x.XXX, x.XXX	x.XXX, x.XXX	x.XXX, x.XXX
		Difference in Proportion	--	x.XXX	x.XXX	x.XX	x.XXX
		p-value ^c	--	0.XXXX	0.XXXX	0.XXXX	0.XXXX
	2	...					
	3	...					
Per Protocol Population					

^a Responder is defined as subjects with at least a 4-fold rise in antibody compared to pre-dose 1.^b 95% confidence intervals are from the Wilson score method without continuity correction.^c P-values were calculated using Fisher's Exact Test.

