### **10.5.3 Analysis of Immunogenicity Data**

Immunogenicity summaries will include all participants who received at least one study vaccination and contributed both pre- and at least one post-study vaccination blood sample for immunogenicity testing for which valid results were reported. Antibody levels will be summarized graphically and numerically. Individual time trends will be visualized as will reverse cumulative distribution plots. Numbers and proportions of participants with seroconversion, defined as a fourfold rise from baseline, will be presented along with 95% CIs by time point and study group. Statistical summaries will include geometric means, geometric mean fold-rise, mean, median, standard deviation, minimum, and maximum by time point and study group.

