3.3. Study Definitions and Derived Variables

Seroconversion is defined as a fourfold rise from baseline.

Clinical laboratory evaluations, vital signs, reactogenicity, and immunogenicity will be assessed on the day of, prior to the first study product injection (Day 1) to establish baseline. If a single ELISA result is below the lower limit of quantification (LLOQ) or above the upper limit of quantification (ULOQ) then the result will be imputed as LLOQ or ULOQ, respectively. If both ELISA results are below LLOQ, then the value will be imputed as $\frac{1}{2} \times \text{LLOQ}$. If both ELISA results are above ULOQ, then ULOQ will be reported.

Any medical condition that is present at the time that the subject is screened will be considered baseline and not reported as an AE. However, if the existing severity of any pre-existing medical condition increases, it will be recorded as an AE.

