6. GENERAL STATISTICAL CONSIDERATIONS

6.1. General Principles

All continuous variables will be summarized using the following descriptive statistics: n (non-missing sample size), mean, standard deviation, median, maximum, and minimum. The frequency and percentages (based on the non-missing sample size) of observed levels will be reported for all categorical measures. In general, all data will be listed, sorted by treatment and subject, and when appropriate by visit number within subject. All summary tables will be structured with a column for each treatment in the order (Group A, Group B, Group C, Group D, Group E) and will be annotated with the total population size relevant to that table/treatment, including any missing observations. If the table including all treatment groups in one table results in the table being too wide, separate tables will be made for each treatment group.

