11. IMMUNOGENICITY

11.1. Secondary Immunogenicity Analysis

11.1.1. ELISA (anti Sm-p80 Total IgG)

Antibody responses, measured by total IgG production to the recombinant Sm-p80 protein using ELISA will be presented at baseline (Day 1) and by study day (Days 8, 29, 36, 57 for all treatment groups; additionally Days 64, 85, 181 for Groups A, B, D, and E, and Days 180, 187, 208, 304 for Group C) using descriptive statistics in [Table 15](#) (mITT immunogenicity population). For post-baseline timepoints, geometric mean fold rise (GMFR) and the proportion of subjects with at least a 4-fold rise will be presented with 95% confidence intervals for mITT population in [Table 16](#) (mITT immunogenicity population). The ELISA seroresponse (at least 4-fold rise) rates at 28-days post vaccination will be compared between Group A vaccine group and each treatment group using Fisher's Exact Test ([Table 17](#)). Confidence intervals for proportions are calculated using Wilson Score methodology without continuity correction. Confidence intervals calculated for GMT and GMFR follow a t-distribution.

Antibody responses will be adjusted for baseline. Reverse cumulative distributions (RCD) curves will be presented with separate panels for each timepoint for mITT population in [Figure 2](#). Graphs of Geometric Mean Anti-Sm-p80 ELISA responses over time will be presented in [Figure 3](#). Individual time trends for each Anti-Sm-p80 ELISA will be presented in [Figure 4](#).

Results of individual total IgG immunogenicity responses, scheduled and unscheduled, will be presented in [Listing 9](#).

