13. REPORTING CONVENTIONS

P-values ≥ 0.001 and ≤ 0.999 will be reported to 3 decimal places; p-values less than 0.001 will be reported as “ < 0.001 ”. The mean, standard deviation, and other statistics will be reported to 1 decimal place greater than the original data. The minimum and maximum will use the same number of decimal places as the original data. Proportions will be presented as 2 decimal places; values greater than zero but < 0.01 will be presented as “ < 0.01 ”. Percentages will be reported to the nearest whole number; values greater than zero but $< 1\%$ will be presented as “ < 1 ”; values greater than 99% but less than 100% will be reported as $> 99\%$. Estimated parameters, not on the same scale as raw observations (e.g. regression coefficients) will be reported to 3 significant figures.

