14.2 Efficacy/Immunogenicity Data

14.2.2 Efficacy/Immunogenicity Response Figures by Measure, Treatment/Vaccination, and Time Point

Figure 2: Reverse Cumulative Distribution of Anti-Sm-p80 ELISA Total IgG Results by Time Point and Treatment Group, mITT Immunogenicity Population

[**Implementation Note:** Figure will be paneled by scheduled time point: 7 and 28 days after each vaccination, and 124 days after the last vaccination. The y-axis will be the “Percent of Subjects (%)” with a max of 100 and the x-axis will be “Baseline-Adjusted Concentrations (OD₄₅₀)”. Each treatment group will have its own marker type and color. A legend will be included containing each treatment group and dosage if enough space available, e.g. Group A would be displayed as “Group A: 100 µg Sm-p80 (unadjuvanted)”. Otherwise treatment group only will be shown.]

Figure 2: Reverse Cumulative Distribution of Anti-Sm-p80 ELISA Total IgG Results by Time Point and Treatment Group, mITT Immunogenicity Population (continued)

Pseudo Code:

```

ods select CDFPlot;
proc univariate data= dsn;
  by trta stdy;
  cdfplot elisa; /*baseline-adjusted results*/
  ods output CDFPlot= _cdf;
data cdf;
  set _cdf;
  cdf = ecdfy; /*standard CDF*/
  cdf2 = 100 - cdf; /*complimentary (reverse) CDF*/
  elisa = ecdfx; /*baseline-adjusted results*/
run;

```

Figure 2: Reverse Cumulative Distribution of Anti-Sm-p80 ELISA Total IgG Results by Time Point and Treatment Group, mITT Immunogenicity Population (continued)

Figure 3: Geometric Mean Anti-Sm-p80 ELISA Total IgG Response Over Time by Treatment Group with 95% Confidence Intervals, mITT Immunogenicity Population

[Implementation Note: The y-axis will be “Baseline-Adjusted Concentrations (OD₄₅₀)”, and the x-axis will be actual study day labelled as “Study Day” with tick marks on 7-days post vaccination, 28-days post vaccination, and 124-days post last vaccination. Each treatment group will have its own marker type and color consistent across all figures. A legend will be included containing each treatment group and dosage if enough space available, e.g. Group A would be displayed as “Group A: 100 µg Sm-p80 (unadjuvanted)”. Otherwise treatment group only will be shown.]

[figure not shown]
[figure not shown]

Figure 4: Individual Time Trends of ELISA Total IgG Response by Treatment Group, mITT Immunogenicity Population

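### SAP Table 15's pseudo code leaves the minimum and maximum on the natural-log scale beside a titre-scale GMT, and the labels on Figures 2 to 4 do not match the antibody endpoint

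*SAP*

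**What the plan says.** **Table 15 (SAP Appendix 1, section 14.2).** For each visit and group the mock-up has rows for n, GMT with 95% CI, mean, SD, median, and minimum with maximum. The pseudo code takes the natural log of the analysis value and passes that log to PROC MEANS as the only analysis variable. It outputs n, mean, SD, median, maximum, minimum and the confidence limits. It exponentiates the mean and the two limits. The range cell is then built as "gmt_mm = ' ('||strip(min)||', '||strip(max)||')'; /*(Min, Max", with no exponentiation.

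**What the text asks for.** Protocol 10.5.3: "Statistical summaries will include geometric means, geometric mean fold-rise, mean, median, standard deviation, minimum, and maximum by time point and study group". SAP 6.1: "All continuous variables will be summarized using the following descriptive statistics: n (non-missing sample size), mean, standard deviation, median, maximum, and minimum". SAP 13: "The minimum and maximum will use the same number of decimal places as the original data".

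**Figures 2 to 4.** SAP 11.1.1 says "Antibody responses will be adjusted for baseline" and gives no formula. The implementation notes for Figures 2 and 3 label the axis "Baseline-Adjusted Concentrations", with OD450 in brackets. Figure 2's code has "cdfplot elisa; /*baseline-adjusted results", and nothing derives that variable. The secondary endpoint in SAP 3.2.2 is a geometric mean titre. Protocol 7.2.2.1 treats the optical density as the plate reading from which an endpoint titre is calculated. Figure 4's note does use a titre axis, but names CSP as the antigen.

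**The concern.** The code puts two scales in one column of one table without saying so. A reader would see a GMT in titre units and, a few rows below, a range in log units. With nine participants per group, the range and median are what a reader uses to judge spread, so a wrong range is a real reporting error in a table for a secondary endpoint.

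Table 15 and Figures 2 to 4 are all on the SAP 6.2 list for the two interim analyses, which use cleaned but unlocked data. SAP 6.6 allows those reports to feed abstracts and presentations, so an uncorrected row or label could be public before the final analysis.

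**Working it through.** The plan gives no figure of its own to reproduce here. The check traces the code and then runs its steps on assumed data.

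**1. Scale of each Table 15 quantity, followed literally**

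| Quantity | Source in the code | Exponentiated? | Scale |
|---|---|---|---|
| GMT | mean of log titre | yes | titre |
| 95% limits | limits for mean of log titre | yes | titre |
| Minimum, maximum | min and max of log titre | no | natural log |
| Mean, SD, median | same log-scale output | not assigned to a cell | natural log if filled from this output |

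**2. Illustration.** Assumption: n = 9, titres 100, 400, 400, 1600, 1600, 1600, 6400, 6400, 25600. The fourfold spacing follows the dilution series in Protocol 7.2.2.1. The starting value of 100 is assumed.

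- Mean of logs = 7.378, SD of logs = 1.698, median of logs = 7.378.
- GMT = exp(7.378) = 1600.
- 95% CI = exp(7.378 ± t(0.975, 8) × 1.698/√9) = (433.8, 5900.8).
- Range cell as coded: ln(100) = 4.6052 and ln(25600) = 10.1503, or (4.6, 10.2) at the mock-up's one decimal.
- Range on the titre scale: (100, 25600).
- Mean, SD and median on the titre scale: 44100/9 = 4900, 8133 and 1600. The coded output holds 7.38, 1.70 and 7.38.

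**3. Sensitivity to the assumed titre level**

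| Assumed titres | GMT | Range as coded | Range on titre scale |
|---|---|---|---|
| 10 times lower | 160 | (2.3, 7.8) | (10, 2560) |
| as in step 2 | 1600 | (4.6, 10.2) | (100, 25600) |
| 64 times higher | 102400 | (8.8, 14.3) | (6400, 1638400) |

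In all three sets the printed maximum lies below the GMT, which cannot happen on one scale.

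**4. Why exponentiating every row is not the remedy.** It would recover the minimum and maximum exactly, because the log is monotone. For the mean it would return the GMT (1600, not 4900), and for the SD it would give a geometric SD. Those rows need the untransformed titre.

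**5. Figures 2 and 3.** SAP 6.4 plans no covariate adjustment, so the adjustment is not a model term. SAP 3.3 defines no adjusted value. The baseline-relative responses that the SAP does define are fold rises: seroconversion in SAP 3.3, and the GMFR against pre-dose 1 in SAP 11.1.1 and Table 16, coded from `mchg`. Neither an OD450 unit nor the word concentration fits a fold rise or a titre.

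**The case against.** The strongest reply is that this is mock-up code under a heading about GMTs, and the GMT part is right. A maximum below the mean gives itself away, so a programmer would probably catch it. The code formats only the GMT string and the range; it never places the mean, SD or median in the table. Nor does the text fix the scale outright: Protocol 10.5.3 and SAP 6.1 list statistics without naming one, and SAP 13 sets decimal places. All of this stands, and it limits the severity. It does not make the coded range right. The row has no log label and shares a column with titre-scale values. A titre scale remains the sensible reading of a protocol that lists mean, median, SD, minimum and maximum alongside geometric means.

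On the figures, the reply is that fold rise is the only baseline-relative response defined, so the missing formula is mostly missing detail. That also stands; what remains is a label that contradicts the endpoint.

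A reader might go further and infer that Figure 3 would overstate responses. SAP 3.3 says "If both ELISA results are below LLOQ, then the value will be imputed as" half the LLOQ, so a participant below the LLOQ on both replicates at Day 1 and again later would have a difference of zero, which cannot enter a geometric mean; dropping such participants would leave only those who rose. The documents do not support that conclusion. They nowhere define the adjustment as a subtraction or provide for dropping zeros, and any size for the effect would need an assumed LLOQ and an assumed share of non-responders.

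**Conclusion.** The Table 15 error is explicit in the code and minor. Followed literally, the minimum and maximum are natural logs beside a titre-scale GMT. That the error occurs does not depend on the assumed titres; only its displayed size does. For the mean, SD and median the claim is narrower: the log-scale output is their only coded source.

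The OD450 label on Figures 2 and 3 and the antigen name in Figure 4 are label errors, and the undefined baseline adjustment is a gap in detail. The GMT with its CI, the GMFR and the seroconversion results are unaffected. No claim is made that Figure 3 would overstate responses.

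**What to change.** - **Table 15 code:** compute mean, SD, median, minimum and maximum from `aval`; keep `log_aval` for the GMT and its CI only.
- **SAP 11.1.1:** add one sentence stating that baseline-adjusted means fold rise from Day 1, using `mchg` as in Table 16.
- **Figures 2 and 3:** derive `elisa` in Figure 2 from that definition, plot the same quantity in Figure 3, and relabel both axes as fold rise.
- **Figure 4:** change the antigen in the axis label from CSP to Sm-p80.

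The cost is edits to SAP text, labels and pseudo code. No new data or analyses are needed. Any interim output already produced from this code should have its range row and figure labels checked.
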